- Significant safety issues that are likely to (or have the potential to) affect to a significant degree the safety or rights of participants or the reliability and robustness of the data generated in the clinical trial.
- Urgent safety measures are implemented to remove or prevent a significant safety issue.
- Safety reports relating to the clinical trial's continuation, suspension, or discontinuation for safety reasons.
- Non-compliance with the protocol, SOPs, GCP, and applicable regulatory requirement(s) significantly affects or has the potential to affect human subject protection or reliability of trial results significantly.
- Participant complaints or concerns were received concerning the conduct of the research.
- Significant modifications to the clinical trial that is likely to affect to a significant degree the safety or rights of participants or the reliability and robustness of the data generated in the clinical trial.
- Addition of participating trial sites, contractual arrangements at participating sites or modifications to legal agreements.
- The intention is to conduct the trial in other countries.

4. Trial Objectives and Purpose

This project aims to characterise the effect and time course of topical anti-allergy treatments on ocular surface dendritic cell density, morphology, and topographical distribution, and the relationships with changes in signs and symptoms of allergic conjunctivitis.

The research question that this study seeks to address is:

Do different therapeutic topical eyedrops (e.g., combination antihistamines and mast cell stabilisers versus corticosteroids) have different effects and time course on ocular surface dendritic cell density, morphology, and topographical distribution in allergic conjunctivitis patients?

The primary endpoint of the trial is the change in dendritic cell density (measured by counting their average number in a given area manually) using in-vivo confocal microscopy.

The secondary endpoints are the change in dendritic cell morphology (determined by measuring cell body size and presence of dendrites manually), using in-vivo confocal microscopy, and the change in eye allergy symptoms (including itchy eyes or watery eyes or burning feeling or feeling like there is dirt or grit in your eyes) and the change in eye allergy signs (including redness or conjunctival chemosis or conjunctival papillae or conjunctival follicles) and the possible relationship between ocular immune system and eye allergy clinical symptoms and signs.

5. Background Information

Allergic conjunctivitis is a group of diseases, that is usually bilateral and caused by the ocular response to various environmental and chemical air pollution allergens. The prevalence of allergic diseases has increased globally in the past few decades, and almost 1 in 5 Australians (19.6% of the total population) report some form of allergy [1-4]. The prevalence of ocular allergy is increasing worldwide, affecting individuals' quality of life, and causing a significant socioeconomic burden [5-8]. In a recent epidemiological survey of allergy prevalence in the US, 15 - 40% of the population reported having at least one ocular allergy symptom and were classified to have allergic conjunctivitis [9]. Allergic conjunctivitis can be managed using a range of options beginning with allergen avoidance and progressing to more complex treatments, including topical pharmacological agents such as decongestants, antihistamines, mast cell stabilisers, corticosteroids, non-steroidal anti-inflammatory drugs, and immunosuppressive agents [10-17].

Ocular dendritic cell play a substantial role in initiating the immune response in the setting of ocular allergies by capturing and processing antigens in peripheral tissue and migrating from the affected tissue to the lymph nodes via lymphatic vessels [18]. Once inflammation occurs, the phenotype of dendritic cell undergoes rapid change, antigen-capturing capability declines, and T-cell stimulation function increases [19]. However, the changes in ocular surface dendritic cell density and morphology were not associated with changes in ocular allergy symptoms or signs in the milder and severe forms of ocular allergy [20-21].

In a recently published article, dendritic cell density was higher in participants with allergic conjunctivitis at the corneal centre, corneal periphery, limbus, and conjunctiva but not at the inferior whorl, compared to controls [21]. Dendritic cell density was highest at the limbus followed by the corneal periphery and the lowest density was at the conjunctiva, and there was no difference between the corneal centre and the inferior whorl [21]. Dendritic cell morphology assessment was based on cell body size (small, medium, large), and the presence of any dendrites, the presence of long dendrites, and the presence of thick dendrites [21]. At corneal centre, dendritic cell had a larger cell body size, and there was a higher percentage of dendritic

cell with dendrites and with long dendrites in the allergic conjunctivitis group [21]. Cell body size, the presence of long dendrites and the presence of thick dendrites were not significantly different between groups at other locations [21]. When allergic participants were symptom free, corneal dendritic cell body size was smaller and there were fewer dendritic cell with long dendrites [22]. At the bulbar conjunctiva, dendritic cell density was reduced during the symptom-free phase but did not change in morphology [22].

The effect of the treatment of ocular surface disease on dendritic cell parameters has rarely been investigated [20-25]. Only two studies investigated these changes in allergic disease, specifically in vernal keratoconjunctivitis [24, 25]. Both studies reported a significant decrease in dendritic cell density, alterations in morphology, and in the presence of dendrites after starting the treatment. Liu et al. examined the dendritic cell density, distribution, and morphology of 35 vernal keratoconjunctivitis patients at the corneal limbus, peripheral cornea, and bulbar conjunctiva and found a significant decrease in dendritic cell density at the bulbar conjunctiva (after one month of treatment) and at the limbus and peripheral cornea (after 3 and 6 months of treatment) in patients treated with fluorometholone 0.1% (a corticosteroid eyedrop) or cyclosporine 0.5% (an immunosuppressant eyedrop) compared to baseline measurements [24]. At the end of the Liu study following treatment, dendritic cell appeared less reflective and had a smaller cell body size and dendrites or no dendrites [24]. Wan et al. found a significant decrease in all dendritic cell characteristics at the palpebral conjunctiva after two weeks of treatment using topical tacrolimus 0.1% (an immunosuppressant eyedrop) on 17 patients with tarsal vernal keratoconjunctivitis compared to baseline measurements [25]. After eight weeks of treatment, dendritic cell appeared as bright large cell without dendrites [25].

Overall, there is a paucity of evidence on the time course and effect of different treatments of allergic conjunctivitis on dendritic cell density and morphology, particularly for the more common and often milder forms of the disease such as allergic conjunctivitis. In addition, previous studies have not investigated or compared anti-allergy treatments. Moreover, the relationships between the time course of changes in dendritic cell characteristics and that of ocular symptoms and signs following anti-allergy treatment have not been explored.

This research is essential because it will help to fill the gaps in the current knowledge by exploring the time course effect of commonly used commercially available topical therapies (a combination antihistamine and mast cell stabiliser and a corticosteroid eyedrop) on dendritic cell density and morphology in allergic conjunctivitis. Dendritic cell density, morphology, and topographical distribution may serve as biomarkers of ocular allergy. Understanding the effect of different topical treatments on ocular dendritic cell will enhance our knowledge of the optimal treatment paradigms for allergic conjunctivitis and provide a potential future avenue for personalising the treatment of ocular allergies.

References

1. Rosario, N. and L. Bielory, *Epidemiology of allergic conjunctivitis*. Current Opinion in Allergy and Clinical Immunology, 2011. 11(5): p. 471-476.
2. Cook, M., et al., *The economic impact of allergic disease in Australia: not to be sneezed at*. 2007, Australasian Society of Clinical Immunology and Allergy (ASCI). p. 41.
3. D'Amato, G., et al., *Meteorological conditions, climate change, new emerging factors, and asthma and related allergic disorders. A statement of the World Allergy Organization*. World Allergy Organization Journal, 2015. 8(1): p. 1-52.
4. Wong, G.W.K., T.F. Leung, and F.W.S. Ko, *Changing Prevalence of Allergic Diseases in the Asia-Pacific Region*. Allergy, Asthma & Immunology Research, 2013. 5(5): p. 251.
5. Pitt, A.D., et al., *Economic and quality-of-life impact of seasonal allergic conjunctivitis in Oxfordshire*. Ophthalmic epidemiology, 2004. 11(1): p. 17-33.

6. Smith, A.F., et al., *The economic and quality of life impact of seasonal allergic conjunctivitis in a Spanish setting*. Ophthalmic Epidemiology, 2005. 12(4): p. 233-242.
7. Miyazaki, D., et al., *Epidemiological aspects of allergic conjunctivitis*. Allergology International, 2020. 69(4): p. 487-495.
8. Dupuis, P., et al., *A contemporary look at allergic conjunctivitis*. Allergy, Asthma & Clinical Immunology, 2020. 16(1): p. 5.
9. Singh, K., S. Axelrod, and L. Bielory, *The epidemiology of ocular and nasal allergy in the United States, 1988-1994*. Journal of Allergy and Clinical Immunology, 2010. 126(4): p. 778-783.e6.

To limit bias, the trial is double-blind, keeping all participants, investigators, and all staff involved in the conduct of the trial blinded to the treatment administered. Eligible participants for this trial will be randomly assigned (based on a pre-determined computer-generated list) to 3 groups to receive either of the study interventions. All interventions are supplied as unit dose unpreserved formulations commercially available in Australia and registered on the ARTG. Intervention categories will be pre-packed in sealed envelopes and randomly labelled (intervention A, intervention B, and intervention C). Each envelope will have a sufficient amount of dosage for the treatment period.

- A schematic diagram of trial design is shown in Figure 2.

[figure not shown]

Figure 2 Trial flow diagram

8. Sample Size

The plan is to enroll 90 subjects to complete the trial.

The overall sample is comprised of the following samples from each of the participant groups:

1. **Participant Group 1** [Topical antihistamine + mast cell stabiliser]: [30 participants]
2. **Participant Group 2** [Topical corticosteroid]: [30 participants]
3. **Participant Group 3** [Topical ocular lubricant]: [30 participants]

Sample size calculation was undertaken using GPower 3.1. The nominated sample is based on based on the expected effect size at the central cornea dendritic cell density (0.512), from a previous study [1], alpha (0.05), and power of (0.8). The sample size will be 25 participants in each arm. The sample size will be adjusted by 20% to compensate for expected withdrawals. Therefore, the total sample size would be 90 participants for all arms, 30 participants in each arm, to ensure 75 participants complete the study after accounting for 20% drop out rate. This sample size is sufficient to meet the research aims and will address all the research questions. By this sample size, the power calculation reveals that this sample size will allow for statistically significant results.

1. Tajbakhsh, Z., et al., *Increased dendritic cell density and altered morphology in allergic conjunctivitis*. Eye (Lond), 2023.

9. Selection and Withdrawal of Subjects

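### Section 8's 25 per arm does not follow from its stated inputs for the between-arm comparison; if 0.512 is a standardised mean difference, simple two-arm power is about 43%, not 80%

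*Protocol*

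**What the plan says.** Section 8 (Sample Size) gives the inputs as the "expected effect size at the central cornea dendritic cell density (0.512), from a previous study [1], alpha (0.05), and power of (0.8"), and concludes: "The sample size will be 25 participants in each arm". It raises this by 20% to 30 per arm (90 in total) so that 75 complete. On method it says only: "Sample size calculation was undertaken using GPower 3.1". The section closes by asserting that the number suffices for the aims and for every research question, and that "this sample size will allow for statistically significant results".

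The design (Section 7) is three parallel arms, randomised 1:1:1. The research question in Section 4 is comparative: "Do different therapeutic topical eyedrops (e.g., combination antihistamines and mast cell stabilisers versus corticosteroids) have different effects and time course". The primary endpoint is change in dendritic cell density. Section 18 plans a linear mixed model for log density with pairwise comparisons between groups.

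The reference given for 0.512 is, by its title, a study of increased dendritic cell density in allergic conjunctivitis. Section 5 describes a comparison with controls in which "dendritic cell density was higher in participants with allergic conjunctivitis at the corneal centre" and at other sites.

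**The concern.** A power statement should refer to the comparison the trial will make. Here that is a difference between independent arms, which for a given standardised effect needs far more participants per arm than a within-group change does. The figure of 25 looks too small for an effect of 0.512 in a two-arm contrast.

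If so, the protocol promises 80% power for its primary question without a calculation that supports it. A null result would then be read as evidence that the eyedrops do not differ, when the trial may have been more likely than not to miss the effect it assumed.

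There is a second question about what 0.512 measures. A difference between allergic and non-allergic eyes is not a treatment effect. Using it as one would assume that an active drop removes the whole disease difference relative to lubricant. That needs a justification, and none is given.

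**Working it through.** **Inputs (Section 8):** effect size 0.512, alpha 0.05, power 0.80, stated result 25 per arm. Test, sidedness and metric are not stated, so several were tried, using exact noncentral t and F distributions.

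**1. Reproducing 25.** One-sample or paired t-test: df = n − 1, noncentrality = 0.512√n.
- One-sided, n = 25: noncentrality 0.512 × 5 = 2.56, power 0.8001. At n = 24, power is 0.785. So n = 25 is an exact match.
- Two-sided: n = 32.

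**2. Two independent arms.** df = 2n − 2, noncentrality = 0.512√(n/2).
- 80% power needs 61 per arm two-sided (power 0.801) or 48 per arm one-sided (0.801).
- At n = 25: noncentrality 0.512 × √12.5 = 1.81; power 0.426 two-sided, 0.556 one-sided.
- If all 30 per arm completed, two-sided power would be 0.496. A 20% loss from 30 leaves 30 × 0.8 = 24, with power 0.412.

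**3. Three-arm one-way ANOVA.** df = 2 and 3n − 3, noncentrality = 3n f².
- f = 0.512: 14 per arm. At 25 per arm, power is 0.980.
- f = 0.512/2 = 0.256 (the usual conversion from d for two groups): 51 per arm. At 25 per arm, power is 0.479.

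None of the between-arm calculations in steps 2 and 3 returns 25.

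**4. What 25 per arm can detect.** Solving step 2 (two-sided 5%, n = 25) for 80% power gives a standardised difference of 0.81.

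**5. What modelling could add.** The protocol gives no correlation, so ρ is an assumption. With m post-baseline visits averaged, baseline adjustment, the same correlation ρ between all visits, and a constant effect of 0.512 at each visit, the variance factor is V = (1 + (m − 1)ρ)/m − ρ², and the effective difference is 0.512/√V. For example, m = 2 and ρ = 0.5 give V = 0.75 − 0.25 = 0.50 and 0.512/√0.50 = 0.724. Two-sided power at 25 per arm:

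| Visits averaged | ρ = 0.5 | ρ = 0.6 | ρ = 0.7 |
|---|---|---|---|
| 1 | 54% | 60% | 70% |
| 2 | 71% | 76% | 84% |
| 3 | 78% | 83% | 89% |

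With a single post-baseline visit, 80% is reached at ρ of about 0.77. With two or three visits it is reached at a lower correlation.

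**The case against.** Three objections have force.

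*The origin of 25 is not stated.* A reader might infer from the exact match that the sponsor ran a one-sided paired test. The protocol does not say so, and the match is not unique once repeated-measures options are allowed. A three-group repeated-measures between-factor calculation with f = 0.256, six measurements and a correlation a little below 0.4 also lands at about 25 per arm. The protocol states none of those inputs either. So the paired origin remains an inference; the point does not need it.

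*The metric is not stated.* A reader might infer that the trial simply has 43% power. That holds only if 0.512 is a standardised mean difference. Read as Cohen's f, 25 per arm gives 98% power for the overall test, although 14 per arm would then have been enough and 25 would still be unexplained. The mean-difference reading is the natural one, because the cited title and the background point to a two-group contrast. The link is not certain: the citation number that the background gives for that contrast leads, in its own reference list, to a different study.

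*The planned analysis may be more efficient.* Confocal imaging is scheduled at baseline and five later visits, and a mixed model is planned. A reader might infer that 80% is out of reach without a correlation near 0.77, but that applies to one post-baseline visit only. Averaging two or three visits gives about 71–89% at correlations of 0.5–0.7. This requires an effect that is constant from visit to visit, which is favourable in a trial that asks about time course. Section 18 does not spell out visit or baseline terms, though a separate analysis plan may.

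None of this rescues Section 8 as written. It claims 80% from three inputs and relies on no correlation, number of visits or adjustment.

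**Conclusion.** The concern holds. The stated 25 per arm does not follow from 0.512, alpha 0.05 and power 0.8 under any simple comparison between arms, whether 0.512 is read as a mean difference or as Cohen's f.

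The size of the shortfall is conditional. With 0.512 as a standardised mean difference, and one pair of arms compared two-sided at 5% at one time point without baseline adjustment, power is about 43% against the stated 80%, and 61 evaluable per arm would be needed. The documents do not support saying that the trial has 43% power under every analysis, nor that a paired test was certainly used.

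The closing assurance of significant results is wrong under any reading: no sample size guarantees significance, and power is always relative to an assumed effect.

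**What to change.** Keep 90 participants and restate Section 8 for the between-arm contrast, naming the test, sidedness, effect-size metric and comparison. Possible wording, if 0.512 is confirmed as a standardised mean difference:

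*With 25 completers per arm, a two-sided 5% comparison of two arms at one time point, without baseline adjustment, has 80% power for a standardised difference of 0.81. Power for a difference of 0.512 is about 43%.*

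Any gain from baseline adjustment or repeated visits should appear only with its assumed correlation, number of visits and pattern of effect over time. Examples are 54–70% with one post-baseline visit at correlations of 0.5–0.7, and about 71–89% when two or three visits are averaged under a constant effect.

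The sponsor should also state which contrast 0.512 measures and why it can stand for a treatment effect. The two assurances, that the size answers every research question and that it will yield significant results, should be deleted.

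The cost is rewording one section, with no added participants or procedures. The downside is a less favourable stated power.

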All medications and control eyedrops used in this trial will be stored securely at the School of Optometry and Vision Sciences (Rupert Myers building), with access limited to study investigators. All medications and control eyedrops will only be dispensed to participants who meet the eligibility criteria and are randomised to a treatment group in the trial. The Investigator (or his/her blinded designated personnel) will maintain a participants Medicine Dispensing Log detailing the medication numbers and dates of medication dispensed for each participant during the course of the trial. Only trained optometrists are to be delegated these responsibilities.

Participants will be instructed to discard used medications and control eyedrops in the appropriate way as per manufacturer guidelines. Unused medications and control eyedrops will be destroyed at the trial site in accordance with local requirements and when site operating procedures permits after the drug accountability has been finalised and signed-off by the Investigator.

13. Randomisation and Allocation

This study is a single centre, double-blinded, randomised, placebo-controlled clinical trial. Eligible participants will be randomly allocated to one of the three study groups in a 1:1:1 ratio based on a pre-determined computer-generated list to ensure every participant has an equal chance of being allocated to any treatment arm. All interventions that will be used in this trial will come in transparent ampules. Originally labelled intervention ampules will be masked by covering the drug information with opaque labels. Intervention ampules will be removed from the original packaging and pre-packed in sealed envelopes, and randomly labelled (intervention A, intervention B, and intervention C). Each envelope will have instructions of use and a sufficient amount of dosage for the treatment period. Each group will be randomly assigned to receive either topical antihistamine and mast cell stabiliser eyedrops (dual-acting agent) or corticosteroid eyedrops in the treatment group and lubricant eyedrops as the control group. The pre-packing of the eyedrops will be allocated to external personnel (not a member of the investigators' group). The external personnel will be responsible for maintaining the randomisation list. The randomisation process will be held at the School of Optometry and Vision Science. No specific experience or qualification is required by the personnel delegated these responsibilities.

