- SPSS software (version 28.0; SPSS inc.) will be used. Differences in symptoms and signs between treatment groups and the control group will be assessed using the Independent Sample t-test or Mann-Whitney U test, as appropriate. For dendritic cell density, A linear mixed model with effect for individuals will be used to examine differences in (log) dendritic cell density between groups and between corneal and conjunctival locations. Pairwise comparisons between groups and locations will be obtained within the model. P-values for multiple comparisons between locations will be adjusted by Holm's step-down Bonferroni method.
- Mann-Whitney U test (for cell body size) and Fisher's Exact test (for the presence of dendrites) will be used to assess differences in dendritic cell morphology between groups. Friedman, and Wilcoxon Signed Ranked Test (for cell body size) and Cochran's Q Test (for the presence of dendrites) will be used to assess differences in dendritic cell morphology across locations and the p-values for pairwise comparison between locations were adjusted by Holm's step-down Bonferroni method.
- Associations between dendritic cell and ocular surface symptoms and signs will be assessed using a univariate Spearman's correlation coefficient (for dendritic cell density and cell body size) and Mann-Whitney U test (for the presence of dendrites).

19. Data Handling, Ownership and Access

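### Section 8's 25 per arm does not follow from 0.512, alpha 0.05 and 80% power for a standard unadjusted between-arm comparison; reaching it needs assumptions the protocol does not state

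*Protocol*

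**What the plan says.** Section 8 (Sample Size) reports: "Sample size calculation was undertaken using GPower 3.1". The inputs are the "expected effect size at the central cornea dendritic cell density (0.512), from a previous study [1], alpha (0.05), and power of (0.8"). The conclusion is "The sample size will be 25 participants in each arm", raised by 20% to 30 per arm and 90 in total. The section then states that the sample is enough for all the research questions and that "this sample size will allow for statistically significant results".

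The comparison the trial makes is between arms. The research question in Section 4 is whether different eyedrops act differently on dendritic cell density, and the primary endpoint there is the change in that density. Section 13 has participants "randomly allocated to one of the three study groups in a 1:1:1 ratio". Section 18 (Statistics) plans a linear mixed model for log density with an effect for individuals, and says: "Pairwise comparisons between groups and locations will be obtained within the model". It specifies no one-sided test and does not mention a baseline covariate.

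**The concern.** Section 8 performs a calculation and draws a conclusion from it, so the conclusion can be tested against its inputs. This is not a detail left for an analysis plan. The usual calculations for comparing randomised arms give numbers well above or well below 25. The simple calculation that lands on 25 is a one-tailed test of change within a single arm, which is not the comparison in Sections 4 and 18.

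At stake is how a null result is read. If 0.512 is a standardised difference between two arms and the analysis gains little from baseline, the trial would more often miss that difference than find it. The protocol would nevertheless present it as having 80% power. A non-significant result could then be taken as evidence that the drops do not differ.

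**Working it through.** **Inputs (Section 8).** Effect size 0.512, alpha 0.05, power 0.80, claimed n = 25 per arm. The index (d, dz or f) and the sidedness are not stated, so each is tried. Allocation is 1:1:1 over three arms (Section 13).

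**Formulas (exact noncentral distributions).**
- Two-sample t: noncentrality d·√(n/2), df 2n − 2.
- Paired t: noncentrality dz·√n, df n − 1.
- Three-arm ANOVA: λ = f²·3n, df 2 and 3n − 3.

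**Step 1. Reproduce 25.** In the paired one-tailed test with dz = 0.512, n = 24 gives power 0.785 and n = 25 gives 0.8001. So 25 is the smallest n that reaches 80%.

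**Step 2. Number needed for 80% power from the three stated inputs alone.**

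| Calculation | n per arm | Power at 25 |
|---|---|---|
| Two-sample t, two-sided, d = 0.512 | 61 | 42.6% |
| Two-sample t, one-sided, d = 0.512 | 48 | 55.6% |
| Three-arm ANOVA, f = 0.512 | 14 | 98.0% |
| Three-arm ANOVA, f = 0.512/2 = 0.256 | 51 | 47.9% |
| Paired t, two-sided (within arm) | 32 | 69.0% |
| Paired t, one-sided (within arm) | 25 | 80.0% |

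Hand check of the first row: 2 × (1.960 + 0.842)² / 0.512² = 2 × 7.85 / 0.262 ≈ 60 by the normal approximation, and 61 with the t distribution.

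**Step 3. What 25 per arm delivers if 0.512 is Cohen's d (two-sided, unadjusted).** Power is 42.6%. With 30 per arm and no loss it is 49.6%. With a Bonferroni correction over three pairs (alpha 0.0167) it is 26% at 25 per arm. The difference detectable with 80% power is 0.81 SD, or 0.94 SD with that correction. 0.81/0.512 = 1.58, so the unadjusted detectable difference is 58% above the planning value.

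**Step 4. Credit for baseline.** The correlation r between baseline and follow-up is assumed, because the protocol gives none.
- *Baseline-adjusted comparison*, effective d = 0.512/√(1 − r²): power at 25 per arm is 54% (r = 0.5), 70% (r = 0.7) and 84% (r = 0.8). Power of 80% needs r of about 0.77. The detectable difference is 0.81 × √(1 − r²), which is 0.70, 0.58 and 0.49 SD.
- *Change from baseline*, effective d = 0.512/√(2(1 − r)): at r = 0.8 this is 0.512/0.632 = 0.81, and n = 25 gives power 0.801 (24 gives 0.784).
- *Baseline-adjusted, one-sided*, r = 0.7: n = 25 gives power 0.803.

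**The case against.** The strongest reply is that between-arm routes to 25 exist. A two-sided comparison of change from baseline with correlation 0.8 gives exactly 25, and change is the primary endpoint. A one-sided baseline-adjusted comparison with correlation 0.7 also gives 25. A fixed-effects factorial ANOVA with f = 0.512, testing the arm-by-visit interaction over 3 arms and the 6 confocal visits in Table 1, gives N = 73, which is 25 per arm after rounding up. These results are correct. A reader might infer from Step 2 that no comparison between arms can produce 25, or that a paired one-tailed test must have been used. The documents support neither. A match at 25 does not identify the test, and the paired reading needs unstated choices too (pairing, one tail, the dz index). The criticism that a within-arm fall cannot be separated from natural remission therefore applies only if that test was the basis; Section 18 plans no such test for density.

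The reply also notes that 43% describes an unadjusted two-sample test, whereas Section 18 plans a mixed model, and that the meaning of 0.512 rests on a source not at hand. That stands as well.

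It does not rescue the figure. Two of the three routes need a correlation that Section 8 does not give, and one of those is also one-sided. The factorial route needs 0.512 to be Cohen's f and treats repeated visits by the same person as independent.

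**Conclusion.** The concern holds in conditional form. From the inputs as stated, 25 per arm is not the answer for a standard unadjusted between-arm comparison: the numbers are 61, 48, 14 or 51, depending on test and index. That part is firm.

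The size of the consequence depends on what 0.512 is. As Cohen's d, two-sided power at 25 per arm is about 43% unadjusted, and 54% to 84% with baseline adjustment at assumed correlations of 0.5 to 0.8. As Cohen's f in a three-arm ANOVA, it is about 98%; the trial would then not be short of power, and 25 would still not follow from the inputs. A reader might infer that the trial is simply underpowered at 43%. The documents do not establish that, because they fix neither the index nor the gain from baseline.

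Separately, no power calculation can assure significant results, so that sentence in Section 8 is wrong on any reading.

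**What to change.** Keep 90 enrolled and amend Section 8:

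1. Redo the calculation for the between-arm comparison of the primary endpoint. Name the test, the sidedness, the effect-size index of 0.512 and any assumed correlation, with its source.
2. Report the resulting power at 0.512 and the difference detectable with 80% power. If 0.512 is Cohen's d, suitable wording is: with 25 completers per arm, a two-sided 5% unadjusted between-arm comparison has 80% power for a standardised difference of 0.81 and about 43% power for 0.512. If credit is taken for baseline adjustment, give the smaller detectable difference together with its assumed correlation, and include the adjustment in the planned model.
3. Delete the sentence promising statistically significant results, and limit the claim about all the research questions to the comparison for which power was calculated.
4. State that a non-significant result is inconclusive for differences below the detectable difference as restated.

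The cost is protocol wording and no extra participants. The downside is that the stated power may become less favourable.
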